7.4 Dosage and administration

Regarding the selection of dose in this study, refer to Section 7.4.1.

Regarding dose(s), route / mode of administration, formulation(s) and duration of treatment(s), refer to Table 7-1 and Table 7-2.

7.4.1 Selection of doses in the study - amended

Each subject will be given 12 mg of copanlisib (i.v. over 1 h).

Rationale for copanlisib 12 mg dose

The 12 mg dose has been chosen (not the Recommended Phase II Dose of 60 mg) to assess the effects of moderate hepatic, severe hepatic or severe renal impairment on copanlisib PK. The rationale for this is the observed dose-linear PK of copanlisib and also the favorable safety profile of 12 mg copanlisib dose in healthy subjects (Human mass balance study 16353). Therefore, the 12 mg dose can be used across all four groups in this study. The results from a clinical study evaluating the effect of the strong CYP3A4 inhibitor itraconazole (as a perpetrator) on copanlisib (as a victim) at 12 mg and 60 mg showed the effect of itraconazole was independent of the dose suggesting the use of 12 mg dose can be predictive of results at higher doses given that the PK of copanlisib is linear.²³

The popPK data for copanlisib demonstrates no statistically significant difference in copanlisib clearance in patients with mild hepatic impairment (total bilirubin [TB] \leq upper limit of normal [ULN] and aspartate aminotransferase [AST] $>$ ULN, or TB $<$ 1-1.5 x ULN and any AST, N = 47) and patients with normal liver function (TB \leq ULN and AST \leq ULN, N = 250).

²³ Paragraph revised as subjects with severe hepatic impairment will be included into the study according to Amendment 1

Further, the popPK data for copanlisib in patients with renal impairment demonstrates no statistically significant difference in copanlisib clearance in patients with mild (CLCr = 60-90 mL/min, N = 112) or moderate renal impairment (CLCr = 30-60 mL/min, N = 58) and patients with normal renal function (CLCr \geq 90 mL/min, N = 125).

Based on the above discussion, the study will be conducted in all subjects at 12 mg dose.

7.4.2 Selection and timing of dose for each subject

Each of the subjects will receive one single dose of 12 mg of copanlisib i.v. over 1 h.

In case of a blood pressure value of \geq 150/90 mmHg before the planned time point of dosing administration will be delayed until recovery to $<$ 150/90 mmHg. Instructions for blood pressure measurements are given in Section 9.6.3.

Antihypertensive medication may be given to control arterial hypertension. Dosing can proceed on the scheduled day if at least 2 consecutive blood pressure values measured at 5 to 10 min interval prior to copanlisib dosing show BP $<$ 150/90 mmHg. Otherwise, dosing must be delayed. Guidance for the treatment of arterial hypertension is given in Section 9.6.1.7.2.

Subject's fasting pre-dose glucose level should be \leq 125 mg/dL (non-diabetic subjects) or $<$ 160 mg/dL (diabetic subjects) before copanlisib infusion (see Section 3, benefit-risk assessment). Guidance for the treatment of transient glucose increase is given in Section 9.6.1.7.1.

Food and drink on the day with dosing will be standardized. For details on meals, see Section 9.2.6.2.

7.5 Blinding

This study will be performed in a non-blinded design, as the primary objective of this trial is the investigation of PK and because the PK results will neither be affected by the subjects nor by the investigator(s).

7.6 Drug logistics and accountability - amended

All study drugs will be stored at the contracted pharmacy ^{PPD} [redacted] or at the study site (^{PPD} [redacted] in accordance with Good Clinical Practice (GCP) and Good Manufacturing Practice (GMP) requirements and the instructions given by the clinical supplies department of the sponsor (or its affiliate/contract research organization [CRO]), and will be inaccessible to unauthorized personnel. Special storage conditions and a complete record of batch numbers and expiry dates can be found in the sponsor's study file; the site-relevant elements of this information will be available in the investigator site file. After receipt check, the responsible site personnel will confirm receipt of study drug in writing. The personnel will use the study drug only within the framework of this clinical study and in accordance with this protocol.

²⁴ Third study site included according to Amendment 1

Receipt, distribution, return and destruction (if any) of the study drug must be properly documented according to the sponsor's agreed and specified procedures.

Written instructions on medication destruction will be made available to affected parties as applicable.

If performing drug accountability implies a potential risk of contamination, a safety process/guidance for handling returned drug will be provided.

7.7 Treatment compliance

The administration of the study medication will be done by a member of the investigator's team. This person will ascertain and document that the subject receives the treatment as planned.

Further information about the subject's treatment compliance can be derived from drug concentration measurements in plasma and urine.

8. Non-study therapy

8.1 Prior and concomitant therapy

All prior medication used within 6 weeks before treatment will be documented (medication history). Copanlisib is metabolized by CYP3A4. Therefore, concomitant use of strong inhibitors of CYP3A4 or strong inducers of CYP3A4 is not permitted from 14 days before the administration of study drug until 7 days after dosing (end of blood sampling period for PK). Refer to Section 6.2 for medication representing exclusion criteria. A list of these medications can be found in Section 16.8 of the protocol.

Use of medication for concomitant therapy is not planned. Especially the use of medication that may have an impact on the study objectives is not permitted. This comprises any medication (including herbal remedies or food supplements), which could affect the pharmacokinetics and / or pharmacodynamics of the study drug. The subjects will be instructed to report any concomitant medication used to the investigator. All concomitant medication will be documented.

The subjects with hepatic and renal impairment will be allowed to continue their medications as long as they are in line with the enrollment criteria.

8.2 Post-study therapy

Subjects will not receive post-study medication by the sponsor. Subjects with renal and hepatic impairment will continue their treatment for their disease as before.

9. Procedures and variables

9.1 Tabular schedule of evaluations

See study flow chart in Section 16.1.

Regarding protocol deviations, the processes and responsibilities defined by the sponsor will be followed. Respective details (e.g. identification and classification of protocol deviations) are described separately.

9.2 Visit description

If not stated otherwise, the measures / actions listed in the following Sections 9.2.1 to 9.2.5 will be performed by or under the supervision of an investigator.

9.2.1 Screening visit - amended

Due to the fact that not all subjects may fulfill the inclusion / exclusion criteria, a higher number of subjects than needed to be valid for the evaluation of the study, will be asked to participate in the screening examinations.

A subject information session will be held. If the (first) screening procedures already start on the same day (same date) as the subject signs the informed consent form, the time of the subject's signature must be recorded in the source documents.

Note: No screening procedures may be performed unless written informed consent has been obtained.

After

- Obtaining the subject's signature on the consent form

the below listed screening procedures will be performed and the respective results will be assessed within 28 days prior to treatment.

- Allocation of screening number, SNR (see Section 6.5)
- Demographic data collection
- Weight, height, body mass index
- Medical and surgical history
- Questioning for special behavior (e.g. smoking history, alcohol consumption, dietary habits)
- Participation in previous clinical studies
- Current and previous medication (relevant medication history)
- Adverse events before start of treatment (e.g. signs / symptoms of the subject; results of physical examination)
- Physical examination (complete)
- Vital signs: blood pressure and pulse rate after resting for at least 10 min in supine²⁵ position and body temperature

²⁵ Corrected to supine position according to Amendment 1 (protocol Version 1.0 specified sitting position)

- 12-lead ECG after resting for at least 10 min in a supine position
- Urine drug screen and alcohol breath test (see Section 16.2 for details)
- Blood and urine sample (fasting) for the laboratory examinations described in Section 16.2
- Virology examination (i.e. HIV, hepatitis B and C virus)
- For hepatic impaired subjects: Child Pugh Scoring and number connection test
- For all subjects: eGFR calculation according to MDRD

Based on the information obtained from the above assessments, i.e. once all results (including laboratory data) are available, the subject's eligibility will be decided upon:

- Eligibility check

No subject may start study treatment unless adherence to all selection criteria as given in Section 6.1 and Section 6.2 is established.

In case of abnormal results caused by intercurrent diseases, short-term treatable conditions or other temporary health disorders (e.g. acute infection, iron deficiency, blood pressure outside defined range), the investigator may decide to repeat the respective screening parameter(s). As a rule, up to two repetitions are acceptable.

As soon as fulfillment of all criteria is confirmed, the subject is included into the trial. In case all subjects are equally qualified, decision will be made casting lots. In case of not being included in the trial the data of the additional subjects will not be listed.

9.2.2 Pre-dose (Study Day -1, relative time: day -01)

The subjects will arrive at the study site in the morning of Study Day -1 (relative time: day -01) (start of in-house period).

The following measures/ actions will be carried out:

- Medical history (update)
- Pregnancy test in blood or urine for women with reproductive potential (including women whose partners are sterilized) (within 7 days prior to dosing)
- Complete physical examination
- Urine drug screen
- Alcohol breath test;
the subjects will be instructed to continue abstaining from alcohol consumption until Day 7
- Urine (Urinalysis) and blood samples (chemistry, hematology and coagulation) in fasted state for safety laboratory examinations. Results of laboratory tests will be checked in the afternoon /evening.
- 12-lead ECG after at least 10 min rest in supine position
- Vital signs: Blood pressure and pulse rate after resting in supine position for at least 10 min and body temperature

- Open questioning for / documentation of AEs and previous/concomitant medication (update)
- Reminder about the restrictions imposed on the subjects
- Final check of applicable inclusion/ exclusion criteria
- Start overnight fasting for 8 h before the procedures for the dosing start (drinking of water and beverages with artificial sweeteners is allowed)

9.2.3 Randomization

Not applicable. For allocation of treatment number, refer to Section 7.3.

9.2.4 Treatment period

In case more than one measure/ action to be performed coincide at a given time point, the following order will be adhered to: ECG, blood pressure / pulse rate, blood sample for PK at defined time points, blood sample for safety.

Any meal will be served after the study-related measures / actions for a given time point have been completed.

9.2.4.1 Dosing and profile day (Study Day 1, relative time: day 00) - amended

The following measures / actions will be performed at the time points given in the study flow chart in Section 16.1.

- Fasting to be continued until the capillary glucose pre-dose is performed (drinking of water and beverages with artificial sweeteners is allowed)
- Abbreviated physical examination
- After a bed rest for at least 10 min, the following baseline measurements will be carried out: 12-lead ECG, vital signs (blood pressure/pulse rate, body temperature), blood sample (fasting capillary blood glucose, PK²⁶)
- Open questioning for / documentation of AEs and previous/concomitant medication (update)
- Low glyceic breakfast at 1.5 h prior to start of the infusion (for details, see Section 9.2.6.2)
- BP will be measured at least 2 times with 5-10 min intervals prior to the administration of the study drug until 2 consecutive values are <150/90 mmHg (see Sections 7.4 and 9.6.3 for further details)
- Study drug administration i.v. (approximately 8 a.m. for the first subject) (see Section 7.4.2)

²⁶ “Protein binding assessment” deleted before dosing according to Amendment 1

- Throughout the day until 12 h p.a.:
 - Capillary glucose 1h after start of copanlisib infusion (end of infusion), 1, 2, 3,²⁷ 6, 8 h after start of infusion, further capillary glucose if necessary
 - Further capillary glucose assessment at the discretion of the investigator (based of previous blood glucose levels)
 - Vital signs (blood pressure/pulse rate, body temperature) after a least 10 min in supine position at 1 h after start of copanlisib infusion (end of infusion) and at 6 h after start of infusion
 - 12-lead ECG after a least 10 min in supine position at 1 h after start of copanlisib infusion (end of infusion) and at 6 h after start of infusion
 - blood sampling for pharmacokinetics at 10 min after start of copanlisib infusion, at 1 h after start of copanlisib infusion (end of infusion) and at 1.5, 2, 2.5, 3, 5, and 8 h after start of infusion
 - blood sampling for protein binding at 1 h after start of copanlisib infusion (end of infusion)
- Urine sampling for pharmacokinetics (0-8 h and 8-24 h)
- Documentation on meal time (whole day)
- Open questioning for and documentation of AEs and update on concomitant medication.

9.2.4.2 Observation day (Study Day 2 and 3, relative time: day 01 and day 02)

The following measures / actions will be performed at the time points given in the study flow chart in Section 16.1.

- Abbreviated physical examination
- 12-lead ECG after at least 10 min rest in supine position
- Vital signs: Blood pressure and pulse rate after resting in supine position for at least 10 min; Body temperature
- Blood and urine sample for safety laboratory examinations
- Blood sampling for PK and protein binding assessment
- Further capillary glucose assessment at the discretion of the investigator (based of previous blood glucose levels)
- Documentation of meal's timing in case of hyperglycemia
- Open questioning for and documentation of AEs and update on concomitant medication.

Provided there are no medical objections, the subjects are released from the ward in the morning of day 02 after having breakfast (48 h post-administration).

²⁷ Capillary glucose at 4h after start of infusion deleted according to Amendment 1

9.2.4.3 Ambulatory visits (Study Day 4 to 6, relative time: day 03 to day 05)

The following measures / actions will be performed at the time points given in the study flow chart in Section 16.1.

- Blood sampling for PK
- Further capillary glucose assessment at the discretion of the investigator (based of previous blood glucose levels)
- Open questioning for and documentation of AEs and update on concomitant medication.

Provided there are no medical objections, the subjects are released.

9.2.4.4 End-of-treatment (Study Day 8 to 11, relative time: day 07(+3))

The following measures / actions will be performed 7+3 days after administration of the study medication:

- Complete physical examination
- 12-lead ECG after at least 10 min rest in supine position
- Vital signs: Blood pressure and pulse rate after resting in supine position for at least 10 min; Body temperature
- Blood and urine sample for safety laboratory examinations.
- Blood sampling for PK
- Open questioning for and documentation of AEs and update on concomitant medication.

Provided there are no medical objections, the subjects are released from the study ward.

If required in case of elevated or decreased laboratory parameters out of the normal range additional visits will be performed after the follow-up visit.

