6.4.2 Replacement - amended

Subjects who drop out may be replaced to obtain a minimum of 30 subjects (8/group except for severe hepatic impairment: 6) valid for PK of copanlisib (i.e., all blood samples for PK should be available up to 1 week [168 h]). Additional healthy subjects may be enrolled to achieve demographic matching between healthy and impaired groups in up to 22 healthy subjects valid for PK of copanlisib (i.e., up to 1 week [168 h]).¹⁸

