9.5 Pharmacokinetics / pharmacodynamics

9.5.1 Pharmacokinetics

9.5.1.1 Drug measurements

Blood samples for pharmacokinetic analyses of copanlisib and its metabolite BAY 84-5795 (M-1) in plasma will be collected at the time points given below and in the study flow chart, see Section 16.1. Urine for PK analyses of copanlisib and its metabolite M-1 will be collected in intervals given below and in the study flow chart (Section 16.1).

Blood samples for PK will be collected before start of infusion as well as at 10 min and 1 h (end of infusion [EoI]), 1.5, 2, 2.5, 3, 5, 8, 24, 48, 72, 96, 120 and 168 h after start of infusion (SoI).

Urine samples for PK will be collected in two sampling intervals from 0-8 and >8 up to 24 h after start of copanlisib infusion.

For all subjects, additional blood sample for evaluation of protein binding of copanlisib will be collected at 1 h after SoI (at EoI) on Day 1, and at 24 h after SoI on Day 2. These samples will be used for determination of fraction unbound and concentrations of total plasma protein, albumin and alpha 1-acid glycoprotein.

Whenever possible, all efforts should be made to adhere to the planned blood sampling schedule for PK. However, based on practical considerations, the following time ranges are provided as guidance:

- Pre-dose samples should be collected within 30 min before SoI.
- The end-of infusion sample for copanlisib and M-1 metabolite should be collected within 5 min after the end of infusion (EoI) of copanlisib for adequate characterization of C_{max} .
- For planned time points ≤ 6 h post-dose, PK samples should be collected within ± 15 min of the planned time.
- For planned time points > 6 h and ≤ 24 h, PK samples should be collected within ± 30 min.
- For planned time points > 24 h, the PK sample should be taken within ± 3 h.

It is of importance that the actual date and time of blood sampling are thoroughly documented in the electronic case report form (eCRF) because PK calculations will be based on the actual sampling times relative to dosing times. Deviations from the specified time points will be documented and taken into account when calculating the PK parameters.

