Cumulated substantial deviations of sampling times and/or consecutive, missing PK samples may lead to an insufficient description of the concentration-time profile(s) of the analyte(s), and thus affect the quality of the PK evaluation of the respective subject(s). In this case these deviations should be classified as “important” and may lead to as declared “validity findings” to the exclusion of the respective subject(s) from the PK analysis set.

Time points for PK samples may be adapted when data from this or another study become available (e.g. by adding up to five blood sampling time points per subject, or moving or deleting sampling time points). The decision on modification of sampling time points as well as the rationale for this will be described in detail in the Clinical Study Report, if applicable.

Regarding handling of the samples collected, refer to Section 16.2. The bioanalytical analyses of the samples will be performed using validated analytical methods. Quality control (QC) and calibration samples will be analyzed concurrently with study samples. The results of calibration samples and QC samples will be reported in the Bioanalytical Report which will be included in the Clinical Study Report for this study. Concentrations are calculated from the chromatographic raw data in accordance with current Bayer guidelines.

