9.5.1.2 Pharmacokinetic evaluation

Non compartmental analysis (NCA)

The PK parameters will be calculated according to the Sponsor’s current guidelines using the pharmacokinetic software WinNonlin (version 5.3 or higher). Based on the concentration time data, the following PK parameters will be calculated.

Parameters based on unbound plasma concentrations will be calculated for copanlisib. The calculation of these parameters ($AUC(0-24)_u$, $AUC(0-168)_u$, AUC_u , and $C_{max,u}$) will be performed by Data Management (see Section 11.3).

Main parameters:

Copanlisib C_{max} , $AUC(0-168)$ and AUC

Additional parameters:

Copanlisib $AUC(0-24)$, $AUC(0-t_{last})$, $t_{1/2}$, t_{max} , t_{last} , V_z , CL , $A_{E,ur}(0-24)$, CL_R , $C_{max,u}$, $AUC(0-24)_u$, $AUC(0-168)_u$, and AUC_u based on average value of unbound fraction in the 1h and 24h samples

BAY 84-5795 (M-1) $AUC(0-168)$, $AUC(0-t_{last})$, AUC , $t_{1/2}$, C_{max} , t_{max} , t_{last} , $A_{E,ur}(0-24)$

Other parameters:

Copanlisib and BAY 84-5795 (M-1) number of points terminal, $\%AUC(t_{last}-\infty)$, R_{start} , R_{end} , C_{last}

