X To be done at the time point indicated

→ To be done continuously, starting from the time point indicated

a Medical History: update only

c After at least 10 min rest in supine position

d In fasted state

f Within 7 days prior to dosing in women with reproductive potential (including women whose partners are sterilized)

g Not mandatory, depends on result of prior capillary glucose results

h End-of-treatment: within 7 + 3 days after administration

i Subjects will receive a low glycemic breakfast at 1.5 h prior to start of the infusion. The breakfast should be completed 1 h prior to start of the infusion. Subjects should remain fasted until 2 h after the end of infusion. During the fasting period after the infusion water may be consumed.

j Only in case of hyperglycemia

k Prior to glycemic breakfast

l Final check of inclusion and exclusion criteria takes place after availability of the safety laboratory results (evening of Day -1 or morning of Day 1).³⁵

³⁵ Footnote added according to Amendment 1

Table 16-1: Study flow chart (continued): End-of-treatment and safety follow-up (all subjects)

Study Day	Relative time	day	End-of	Telephone interview	
			treatment		
			8 (+3)	15 (±3)	31 (+3)
			7 (+3)	14 (±3)	30 (+3)
		Ambulatory follow-up visits	X		
		Complete physical examination	X		
		Vital signs	X		
		12-lead ECG	X		
		Blood sampling			
		- safety (clinical chemistry, hematology, coagulation)	X		
		- PK assessment of copanlisib and M-1	X		
		Urine sampling			
		- Safety ^d (dipstick ± sediment)	X		
		Adverse events	X	X ^a	X ^a
		Concomitant medication	X	X	X

a Any AEs ongoing at Safety Follow-up visit should be followed until resolution or stabilization unless, in the investigator's opinion, the condition is unlikely to resolve due to the subject's underlying disease. All SAEs (including deaths) occurring up to 30 days after the single dose should be reported to the sponsor per usual SAE reporting procedures.

d In fasted state

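### Does the +3-day end-of-treatment window conflict with the 168 h PK sample in a way that matters for AUC?

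*Protocol*

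**What the plan says.** Protocol Section 9.5.1.1 lists the plasma sampling times, ending at 120 h and 168 h after the start of infusion. It adds "For planned time points > 24 h, the PK sample should be taken within ± 3 h", which for the last sample means 165 to 171 h. These ranges are not hard limits: "the following time ranges are provided as guidance".

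The visit descriptions place the 120 h sample in the last ambulatory visit (Study Day 6). The only later visit with a PK draw is end of treatment, Section 9.2.4.4: "The following measures / actions will be performed 7+3 days after administration of the study medication". The flow chart in Section 16.1 agrees. Its end-of-treatment column is headed 7 (+3) and carries the row "PK assessment of copanlisib and M-1". A flow-chart footnote words the visit slightly differently: "End-of-treatment: within 7 + 3 days after administration".

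Other places assume one week. Section 6.4.2 describes a subject valid for PK as one for whom "all blood samples for PK should be available up to 1 week [168 h", and SAP Section 4.2 repeats this. Section 8.1 treats 7 days after dosing as the end of PK blood sampling.

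On deviations, Section 9.5.1.1 says that actual times are used in the PK calculations, and "Cumulated substantial deviations of sampling times and/or consecutive, missing PK samples may lead to an insufficient description" of the profile, which can become a validity finding. Section 9.5.1.2 leaves the calculation to the sponsor's "current guidelines using the pharmacokinetic software WinNonlin (version 5.3 or higher").

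**The concern.** Read side by side, the two schedules overlap for only 3 hours. A site that works from the visit description or the flow chart could draw the last sample on day 10, 72 h after the planned time, and believe it had followed the protocol. A site that draws at 166 h meets the PK guidance but precedes the visit window.

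AUC(0-168) is a primary variable and the parameter used to size the study, and AUC to infinity is also primary. A late draw could matter in three ways:

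- The interval after the 120 h sample grows from 48 h to as much as 120 h, so more of the curve rests on interpolation.
- The last concentration is lower, and the documents give no LLOQ.
- It may be unclear whether the subject counts as valid for PK. Groups have only 6 or 8 subjects, and the interim analysis is triggered by 8 evaluable subjects in each of two groups.

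**Working it through.** **Windows.** Visit window: 7 × 24 = 168 h to 10 × 24 = 240 h. PK guidance window: 168 − 3 = 165 h to 168 + 3 = 171 h. Both hold from 168 to 171 h. That is 3/72 = 4% of the visit window, or 3/6 = 50% of the PK window. Neither share is a probability that a sample will be late. A visit on day 7 at about the hour of dosing meets both texts.

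**Inputs for sizing a late draw.** Terminal half-life 38.2 h, range 16.9 to 72.7 h (Protocol Section 3, Pharmacokinetics). Extrapolated part of AUC 4.8% of AUC(0-168) in Study 16270 (Protocol Section 10.4). Assumptions: mono-exponential decline from time 0 and a quantifiable late sample. The documents do not state the trapezoid rule, so linear and log-linear rules are both considered.

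**Check of the model.** k = ln 2/38.2 = 0.01815 per h. With C(0) = 1: C(120) = 0.1133, C(168) = 0.0474, C(240) = 0.0128. The model tail is 0.0474/(1 − 0.0474) = 5.0% of AUC(0-168), close to the stated 4.8%. The ratio C(240)/C(168) is 0.27 (0.05 at 16.9 h, 0.50 at 72.7 h).

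**AUC(0-168), linear rule.** True area to 168 h = (1 − 0.0474)/k = 52.50. True area from 120 to 168 h = (0.1133 − 0.0474)/k = 3.63.

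- On time: 48 × (0.1133 + 0.0474)/2 = 3.86. Bias (3.86 − 3.63)/52.50 = +0.4%.
- At 240 h: interpolated C(168) = 0.1133 − (0.1133 − 0.0128) × 48/120 = 0.0731. Area 48 × (0.1133 + 0.0731)/2 = 4.48. Bias (4.48 − 3.63)/52.50 = +1.6%.

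| Last sample | Bias in that subject's AUC(0-168), half-life 38.2 h |
|---|---|
| 168 h | +0.4% |
| 192 h | +0.9% |
| 216 h | +1.3% |
| 240 h | +1.6% |

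At 240 h the bias is +0.5% for a 16.9 h half-life and +1.1% for 72.7 h. A log-linear rule gives zero under this model. Anchoring the tail to 4.8% gives +0.42% on time and +1.55% at 240 h for a 38.2 h half-life. Pairing a 4.8% tail with a 16.9 h half-life gives about 25%, but the pairing is not coherent: mono-exponential decline at 16.9 h leaves a tail of only about 0.1%.

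**Effect on a group.** One subject at 240 h instead of 168 h: (1.016/1.004)^(1/8) − 1 = 0.15% for n = 8, and ^(1/6) − 1 = 0.20% for n = 6. If every subject in one group were sampled at 240 h and every control on time, the ratio would move by 1.016/1.004 − 1 = 1.2%. For scale, the plan's 90% CI at an observed ratio of 1 is 0.685 to 1.461 with 8 per group and 0.628 to 1.593 with 6.

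**AUC to infinity.** This variable uses the whole interval to the last sample. Linear rule at 240 h: 120 × (0.1133 + 0.0128)/2 = 7.57, against a true (0.1133 − 0.0128)/k = 5.54. Total AUC is 1/k = 55.1, so the bias is +3.7%, against +0.4% on time. One such subject moves the group geometric mean by (1.037/1.004)^(1/8) − 1 = 0.4% for n = 8, or 0.5% for n = 6. The log-linear rule again gives zero.

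**Who counts.** The documents give a route. Section 9.5.1.1 asks for every effort to keep the PK schedule, has deviations recorded and taken into account, and makes substantial ones possible validity findings. Section 9.1 says deviations are identified and classified under a separate description. SAP Section 5.1 leaves analysis-set membership to the validity review meeting, with the decision documented.

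**The case for a change.** The best argument for a change is that actual sampling times deal with bias but not with counting. Section 9.5.1.1 calls its window guidance and itself refers to the flow chart for sampling times, so it does not plainly override the 7 (+3) heading. Validity for PK is tied to samples up to 168 h, while the PK analysis sets need only a calculable profile. No text says whether one late last sample is a substantial deviation. With 6 to 8 subjects per group, one disputed subject could affect replacement or the date of the interim analysis, which is also the final analysis for two groups. Amendment 1 has already corrected similar mismatches between visit text and flow chart.

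The mismatch itself stands. The counting argument loses most of its force because the case-by-case decision is assigned and documented, and because a fixed rule for one late sample is largely a matter of preference. Neither document defines evaluable precisely in any case, so that doubt does not come from this window. The LLOQ worry cannot be sized without a limit of quantitation. In slow eliminators, a later quantifiable sample would instead extend the observed curve and reduce extrapolation. Splitting the draw from the other assessments could also require a second trip, since Section 9.2.6.2.1 counts a single end-of-treatment visit.

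**Conclusion.** No change to the plan is needed. The visit text and the flow chart lack a cross-reference to the 168 h sampling time. Section 9.5.1.1, the synopsis and Section 8.1 all point to day 7 for the draw, and a visit at 168 to 171 h meets every text. If a draw is late, actual times, deviation handling and the validity review meeting cover it.

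The cost of one draw at the far end of the window is 0.15% to 0.20% in a group geometric mean for AUC(0-168), and about 0.4% to 0.5% for AUC to infinity. Both are about zero if the sponsor's guidelines use a log-linear rule. This rests on mono-exponential decline over the reported half-life range and a quantifiable late sample. A pointer to the 168 h timing could be added if the protocol is reopened for another reason, but it would alter no estimate or conclusion.
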